Effects of the Intervention (Aims 1 and 2): Generalized linear models accounting for repeated measurements over time will be used to estimate the effect of treatment group assignment on each of the outcomes. In modeling, outcomes will be considered at their key time-points with treatment group and the interaction of treatment with time serving as the main explanatory variables. Such a model will allow us to test for differences between treatment and control groups over time while accounting for heterogeneity among subjects at baseline. While the randomized block design should minimize confounding, we will adjust for site and sex to improve precision. Regarding the choice of statistical model, we will use ordinary multiple regression for truly continuous responses, logistic regression for binary responses, and for outcome scales that are not truly continuous or have heavy ties in some of their values, the proportional odds ordinal logistic model. The error structure of the model is assumed to be compound symmetric, and the validity of this assumption will be examined by computing Akaike Information Criteria against other common structures. **Mediation (Aim 3):** To assess direct and indirect effects of potential mediator variables, we will follow steps outlined by MacKinnon and

colleagues to establish mediation. Mediation models will be estimated using the “mediation” package in R. **Moderation (Exploratory Aim 4):** Modifiers of treatment effect over time will be considered by introducing interactions between modifiers and the treatment by time interaction. The model building and validation strategy will otherwise be the same as for Aims 1 and 2.

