The general analysis plan for **Aim 2** will be identical to Aim 1, except indicators of youth outcomes will be considered. Continuous outcomes (e.g., social participation) will be modeled using linear regression, binary outcome (e.g., employment/PSE) will be modeled using logistic regression, and ordinal outcomes (e.g., number of services) will be modeled using proportional odds ordinal logistic regression (or another model, as specified in Aim 1). Time since beginning the VAP-T workshop will be the time scale of interest for all subjects, and we will flexibly model changes over time using restricted cubic splines. Significant changes over time will be assessed using likelihood ratios tests. For continuous outcomes, we will fit separate linear mixed effects models that include a random intercept to account for correlation arising from taking repeated measurements on the same subject over time. In sensitivity analyses we will use the Akaike Information Criterion to compare different models of the longitudinal correlation (e.g. random intercept, autoregressive, unstructured). For binary and ordinal longitudinal outcomes, we will use generalized estimating equations (GEE) and the robust Huber-White sandwich estimator clustering on participant identifier to account for longitudinal correlation. Analyses for Exploratory Aims 2a (using data collected from youth with ASD) and 2b (examining maintenance of treatment effects) will follow this same approach.

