Missing Data. An advantage to our proposed random effects longitudinal models is that they will readily incorporate both missing waves of data and mistimed measurements. In general, we will assume that data are missing-at-random (MAR) for the growth models and missing completely at random (MCAR) for binary and ordinal outcome models estimated using GEE and mediation analysis. Attrition analysis will be used to evaluate these assumptions. Analysis methods will also consider subjects who fail to complete the study (“dropouts”). Indirect information about the dropouts will be obtained by using binary logistic models to predict the probability of dropping out on the basis of all baseline predictor variables. When a variable is a significant predictor of dropout, the distribution of that variable differs for completers and subjects who drop out.

Power/Sample Size: We plan to recruit 180 subjects and after dropout expect to retain 162 subjects through initial post-test (Aim 1) and 152 subjects (76 per treatment group) through the 12-month follow-up (Aims 2 - 4). For power calculations, we consider baseline to post-test changes using the smaller sample size of 152. For continuous outcomes, the size of effect that we will have 80% power to detect will be impacted by the correlation between the pre and post measurement of the outcome. At worst ($r=0$), we will have 80% power to detect a 0.46 sd difference in continuous outcomes. If the correlation is 0.2 or 0.4, we will be able to detect a 0.29 or 0.17 sd difference, respectively. We believe these estimates are conservative because, from our pilot work, correlations between baseline and post-test scores of intervention targets were 0.56 (empowerment), 0.39 (advocacy skills), and 0.57 (knowledge). For binary outcomes, in pilot data, the probability of being employed or in PSE was about 0.5, so under this assumption we will have 80% power to detect a relative risk of 1.44. Regarding Aim 4, we will have 80% power to detect a 0.42 sd modification of the treatment effect assuming a $r=0.2$. All calculations assume a two-sided significance level of 0.05.

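### The SAP assumes MCAR for the binary and ordinal GEE outcomes and plans only diagnostic dropout checks, with no MAR-valid analysis; the GEE test and working correlation are also left unstated

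*SAP*

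**What the plan says.** **Models (SAP, Aim 2).** The SAP states a general rule: "Significant changes over time will be assessed using likelihood ratios tests". Only after that does it separate the outcome types. Continuous outcomes get linear mixed models with a random intercept, with AIC used to compare correlation structures in sensitivity analyses. For the rest: "For binary and ordinal longitudinal outcomes, we will use generalized estimating equations (GEE) and the robust Huber-White sandwich estimator clustering on participant identifier". Employment/PSE is the binary example, and number of services is ordinal by default. No test statistic and no working correlation is given for GEE.

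**Missing data (SAP, Missing Data).** For continuous outcomes, "we will assume that data are missing-at-random (MAR) for the growth models". The stronger assumption, "missing completely at random (MCAR) for binary and ordinal outcome models estimated using GEE and mediation analysis", applies to the others. The follow-up is "Attrition analysis will be used to evaluate these assumptions", together with logistic models that "predict the probability of dropping out on the basis of all baseline predictor variables". No weighting, imputation or other re-analysis is planned, and no action is stated if the check fails.

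**Protocol.** Section 8 (Statistical Considerations) lists linear, logistic and proportional-odds models and then says "The error structure of the model is assumed to be compound symmetric", to be checked by "computing Akaike Information Criteria against other common structures". The parent measures table in section 5 flags the vocational-educational and service-access interviews as primary at 6 and 12 months.

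**Expected loss (SAP, Power/Sample Size).** Of 180 families, 162 are expected at post-test and 152 at 12 months (76 per arm).

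**The concern.** The same families supply both kinds of outcome, so a family that leaves is missing from both. It is hard to justify assuming MAR for one kind and MCAR for the other, except that ordinary GEE needs the stronger assumption. That assumption falls on employment/PSE and number of services, which come from the primary interviews.

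The planned checks diagnose; they do not correct. A dropout model on baseline variables can pick up only the part of dropout that baseline predicts. It cannot show directly that families left because of the youth's status at 6 months, and it states no term for arm. At stake is a possible bias in the 12-month treatment odds ratio, with no planned analysis to reveal or remove it.

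The GEE wording adds to this. GEE has no likelihood, so neither a likelihood-ratio test nor ordinary AIC is available for it, and under MAR dropout the working correlation affects bias as well as efficiency.

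**Working it through.** **1. The plan's own figure.** Inputs from the SAP power section: 76 per arm, control probability 0.50, relative risk 1.44 (so 0.72), two-sided 0.05, 80% power.

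n per arm = [1.96·√(2·0.61·0.39) + 0.8416·√(0.50·0.50 + 0.72·0.28)]² / 0.22² = [1.96·0.6898 + 0.8416·0.6720]² / 0.0484 = 75.97, so 76. The figure reproduces, and nothing here disputes it.

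**2. Expected loss.** 180 − 152 = 28 (15.6%): 180 − 162 = 18 before post-test and 162 − 152 = 10 after it. The SAP does not say how many of the 10 leave after the 6-month visit. Only those have an observed 6-month status that could drive dropout.

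**3. Bias of a working-independence GEE, binary outcome.** Assumed, not in the documents:
- probability 0.5 in both arms at 6 and 12 months (true OR 1.00);
- latent correlation ρ of 0.5 to 0.7 between the two visits;
- loss four times as likely for one 6-month status as for the other, either in one arm only (loss in the other arm unrelated to status) or reversed between arms;
- earlier losses unrelated to outcome.

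Let L be the loss after 6 months. The two loss rates are q and 4q, with q = 2L/5. The excess of one status among those retained is s = 3q/(2 − 5q). With a = arcsin(ρ)/π, which is 0.1667 at ρ = 0.5 and 0.2468 at ρ = 0.7, the observed 12-month probability in the affected arm is p = 0.5 + s·a. The OR is p/(1 − p) for one arm, and its square if the pattern is reversed between arms. The SE of the log OR at 76 per arm is √(8/76) = 0.324.

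| Losses after the 6-month visit | q, 4q | s | Smallest OR (ρ 0.5, one arm) | Largest OR (ρ 0.7, reversed) | Bias in SE |
|---|---|---|---|---|---|
| 5 of 157 | 1.3%, 5.1% | 0.0197 | 0.5033/0.4967 = 1.01 | (0.5049/0.4951)² = 1.04 | 0.04 to 0.12 |
| 10 of 162 | 2.5%, 9.9% | 0.0395 | 0.5066/0.4934 = 1.03 | (0.5097/0.4903)² = 1.08 | 0.08 to 0.24 |
| 28 of 180 | 6.2%, 24.9% | 0.1105 | 0.5184/0.4816 = 1.08 | (0.5273/0.4727)² = 1.24 | 0.23 to 0.67 |

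For an ordinal outcome with six equal categories (assumed; SE 0.285), the middle row also runs from 1.03 to 1.08. The largest shift is then log(1.08)/0.285 = 0.27 SE. Across both outcome types, type I error in that row is 5.1% to 5.9%.

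**4. Dropout alike in both arms.** A large simulated sample used 12-month probabilities of 0.50 and 0.72, 6-month probabilities of 0.50 and 0.62, latent correlation 0.6, and loss of 25% or 6% by 6-month status in both arms. Working independence gave a log OR of 0.946 against a true 0.944, so the odds ratio is essentially unbiased. The relative risk moved slightly: 0.738/0.5225 = 1.41 against 1.44. With all losses after 6 months, the shift in relative risk ranged from 1.41 to 1.47.

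**5. Opposite dropout by arm, all losses after 6 months (same probabilities).** Losses were 26% and 5% by status in controls, and 5% and 22% in the treated arm. Working independence gave a log OR of 0.762 (relative risk 1.34). Exchangeable GEE gave 0.932, and inverse-probability weighting returned a relative risk of 1.44. So the choice of working correlation matters, and a MAR-valid estimator recovers the truth.

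**The case against.** The SAP discloses its MCAR assumption and plans to examine it. The bias is small on any timing consistent with the expected 162 at post-test, and nothing in the documents points to dropout that differs by arm. All of that stands, and it keeps the point minor. It does not supply a corrected estimate if the assumption fails.

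Three stronger readings are tempting, and the documents do not support them.

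- *The tests of the primary outcomes are invalid.* The likelihood-ratio sentence comes directly before the mixed-model text, and the sandwich variance prescribed for GEE already implies a robust test. Harm would need an analyst to ignore that variance. In simulation (latent correlation 0.5 / 0.7, three waves), a likelihood-ratio test from an independence fit rejected 1.1% / 0.4% of the time for treatment-by-time, which is conservative. It exceeded 5% (6.3% / 7.6%) only for a joint treatment test that the sentence does not name.
- *The SAP contradicts the protocol on correlation structure.* The SAP's random intercept carries compound symmetry into the continuous models. That the protocol's error-structure statement also covers GEE is an inference. With complete or MCAR data, the sandwich variance keeps inference valid whatever the working correlation.
- *The odds ratio could be off by a quarter.* The 1.24 needs all 28 losses to follow the 6-month visit, but the SAP expects 18 of them before post-test.

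**Conclusion.** The point holds as a minor one. Key outcomes from the primary interviews rest on MCAR, with diagnostic checks only and no analysis valid under MAR. Bias in the 12-month odds ratio arises only if dropout depends on 6-month status differently by arm. Under the assumed 4:1 pattern and latent correlations of 0.5 to 0.7, it is 1.01 to 1.04 if half of the later losses follow the 6-month visit and 1.03 to 1.08 if all do (at most about 0.27 SE). The range 1.08 to 1.24 is an upper bound that does not fit the SAP's expected timing. If dropout acts alike in both arms, the odds ratio is essentially unbiased and the relative risk can shift a little.

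Continuous outcomes in the mixed models are not affected. Mediation, which the SAP also places under MCAR, and the knowledge score were not assessed. The missing GEE test and working correlation are gaps in wording.

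**What to change.** Pre-specify one analysis of the binary and ordinal outcomes that is valid under MAR, as either:
- multiple imputation by arm, using baseline variables and earlier outcomes; or
- GEE weighted by the inverse probability of retention, from a model with arm and earlier outcomes (with working independence if weights differ by visit).

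Alongside it, amend the wording:
- limit likelihood-ratio tests and AIC to the likelihood-based mixed models;
- name the robust Wald or generalised score test for GEE;
- state the working correlation in advance. Exchangeable would match the random-intercept structure of the continuous models, though it is not formally valid under MAR and does not replace the analysis above.

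The cost is a few sentences and some programming, with no new data. In simulated trials of 180 families with a binary outcome, the mean SE of the 12-month log OR was 0.327 with working independence, 0.319 to 0.323 exchangeable, 0.327 to 0.328 weighted and 0.321 to 0.325 imputed. Precision was therefore essentially unchanged, but this was shown for the binary outcome only. The downside is reliance on a correctly specified imputation or weighting model.

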Next, the program was developed to reflect the availability and eligibility of services in one state (Tennessee); this decision was made because the adult service landscape differs from state to state. In the proposed project, we revise the curriculum to be nationally-relevant, by presenting aspects of each topic that are applicable across states and bringing in local experts to present information relative to their region. We also improve upon our study design by replacing a wait-list control with an active, materials-only control. The control group will receive the same written materials as the treatment group, but will not

receive the group-based training (they will have the option to participate in the training at the end of the study) This design improves upon our pilot work in two ways: (1) it will allow us to test whether receiving written information, without training, has similar benefits as the group-based program; and (2) it is more acceptable to participants. Though participants were not blinded, research staff facilitating completion of the surveys were blinded to experimental conditions.

2. Rationale and Specific Aims

An overview of the current study design is presented here (see Figure 2 below). We propose a multi-site (Nashville, TN; Chicagoland, IL; Madison/Milwaukee, WI) RCT of 180 families to test the effectiveness of ASSIST. Participants will be recruited in two cohorts and randomly assigned to either a treatment or materials-only control condition.

By randomly assigning participants to conditions, we reduce the likelihood of confounders that obscure treatment effects. Recruiting across three sites with diversity in community size, racial/ethnic make-up, and adult service systems will reduce bias due to unrepresentative samples.

We will also examine mechanisms of action and explore moderators of treatment response and barriers to participation. Our sample is sufficient to test our research questions (based on our statistical Power analysis). We will collect data from youth with ASD and their parents, to reduce informant bias. Post-randomization data collection will be conducted by personnel blinded to study condition. Based on existing research, we would expect that parents who receive the written materials might have some increase in knowledge about adult services, but likely not empowerment nor would we expect change in youth outcomes.

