The ASSIST program is a 12-week advocacy training to educate parents of youth with ASD about the adult service system. It is a group training, comprised of didactic instruction, family-sharing activities, case studies, and group discussions. Due to social distancing restrictions during the COVID-19 pandemic, the intervention will be conducted via web-conferencing. The ASSIST program for the proposed study will be directed at each site by an experienced Program Facilitator from the community with knowledge about group processes, person-centered planning, and adult service systems, who will be coached by a member of the study team. The ASSIST program will be delivered in full partnership with the local disability community. In most sessions, the Program Facilitator will be aided by community content experts who present the specifics of each topic. Experts will include representatives from the Parent Training and Information Centers, The Arc, the University Centers for Excellence in Developmental Disabilities, various

government agencies, attorneys, and parents of individuals with ASD. We have tentatively identified (and partially recruited) most of these community experts at each project site.

Finally, we take further steps to ensure that parental advocacy reflects the goals of the youth with ASD by: having a semi-structured discussion with the youth with ASD and their supporters about that youth's hopes, dreams, and goals prior to their parent taking the ASSIST program; developing individualized goals for transition outcomes from those discussions that will be used as an outcome measure; and including the youth with ASD in follow-up data collection to incorporate their perspective.

Specific Aims

Specific Aim 1. To use a multi-site RCT to examine whether ASSIST participation increases the intervention target of parent advocacy ability (defined by parental knowledge about adult service systems, advocacy skills, empowerment, and advocacy activities).

Hypothesis. Relative to a materials-only control group, ASSIST participation will lead to improvements in parental knowledge about adult services, advocacy skills, empowerment, and advocacy activities.

Specific Aim 2. To test whether participating in ASSIST leads to increases in employment, PSE, social participation, and access to services that facilitate these activities (number of services, unmet service needs, barriers), for youth with ASD transitioning from high school to young adulthood.

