Hypothesis. Relative to the materials-only control group, youth whose parents participate in ASSIST will have increased access to services and higher rates of employment, PSE, and social participation at 6-months and 12-months post-intervention.

Exploratory Aim 2a. We will examine whether ASSIST participation leads to enhanced goal attainment (as assessed by parents and youth with ASD), as well as better youth-reported quality of life and fit of employment/educational activities to the youth's skills and interests.

Exploratory Aim 2b. Using data collected 24-months and 30-months after intervention, we will examine whether treatment effects are maintained, strengthen, or wane.

Specific Aim 3. To examine which intervention targets (parent knowledge, advocacy skills, empowerment, advocacy activities) mediate the relations between ASSIST participation and youth outcomes of employment, PSE, social participation, service access, and goal attainment.

Hypothesis. In contrast to other intervention targets changed by ASSIST, parental empowerment will be the mechanism by which ASSIST participation leads to improvements in youth employment, PSE, social participation, service access, and goal attainment.

Exploratory Aim 4. To guide further adaptations of ASSIST, we will explore moderators of treatment response and barriers to participation in the intervention. We will explore factors that could relate to parents' ability to complete the ASSIST program and treatment

response, including: youth's intellectual functioning, pre- vs. post-high school exit, attendance at ASSIST sessions, socio-economic status, parental education, community size, family stress, and number of children with ASD in the family. We will also analyze qualitative data to inform future efforts to increase the accessibility of the ASSIST program for individuals with ASD.

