Aim 3: While evaluating the main effects of interventions is critical to improving outcomes, it is also important to examine mediators of randomized-controlled trials – even those that are unsuccessful – in order to determine how interventions may work^{84,85}. Examining mediators will provide evidence for the mechanisms of change, offering direction for program implementation and future research⁸⁶. To assess direct and indirect effects of potential mediator variables, we will follow the steps outlined by MacKinnon and colleagues^{79,80} to establish mediation. Regression models will be specified to preserve temporal ordering by considering covariates collected at the prior wave and outcomes collected at the current wave. Model-based causal mediation analysis will be proceeded in two steps: (1) specifying the mediator model for the conditional distribution of the mediator given treatment and pre-treatment covariates and (2) specifying the outcome model for the conditional distribution of the outcome given treatment, the mediator, and covariates. Models will be estimated using the mediation package in R which allows for linear, logistic, ordinal, and generalized linear statistical models for both the mediator and outcome models⁸¹. Bootstrapping will be used to estimate a non-parametric 95% confidence interval for the indirect effect. The indirect effect will be statistically significant if the confidence interval does not contain 0. We will conduct sensitivity analyses to evaluate the sequential ignorability assumption, which is also available in the mediation package in R. Furthermore, we will consider sensitivity analyses using structural equations models, and multivariable models adjusting for potential confounders will be used to confirm any findings.

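### Aim 3 hypothesises that empowerment, in contrast to the other parent targets, is the mechanism, but the SAP states no joint model or contrast of indirect effects; and advocacy activities has no post-baseline value before the 6- or 12-month outcomes

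*SAP*

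**What the plan says.** Protocol section 2 names four candidate mediators in Specific Aim 3: knowledge, advocacy skills, empowerment and advocacy activities. The hypothesis reads: "In contrast to other intervention targets changed by ASSIST, parental empowerment will be the mechanism by which ASSIST participation leads to improvements".

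The SAP, Aim 3, fits a mediator model and then an outcome model, described as "specifying the outcome model for the conditional distribution of the outcome given treatment, the mediator, and covariates". Its criterion is "The indirect effect will be statistically significant if the confidence interval does not contain 0". On timing it says: "Regression models will be specified to preserve temporal ordering by considering covariates collected at the prior wave and outcomes collected at the current wave".

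The SAP also cites published steps for establishing mediation, commits to sensitivity analyses of sequential ignorability, and adds two further checks: "we will consider sensitivity analyses using structural equations models", and "multivariable models adjusting for potential confounders will be used to confirm any findings". Neither check names the other targets.

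The parent repeated-measures table (Protocol section 5) gives this schedule for the targets:

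| Target | Waves | Post-baseline value before T2 or T3 |
|---|---|---|
| Empowerment | T0, T1, T3, T4, T6 | T1 |
| Skills; knowledge | T0, T1, T3, T4 | T1 |
| Advocacy activities | T0, T3, T6 | none |

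The T3 entry for advocacy activities carries the key letter for a primary outcome. Specific Aim 1, however, counts it within the intervention target, which is "defined by parental knowledge about adult service systems, advocacy skills, empowerment, and advocacy activities".

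**The concern.** Two parts of the mediation plan do not match what Aim 3 sets out to show.

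- **The comparison.** Testing each indirect effect against zero can show whether empowerment mediates. It cannot show that empowerment mediates in contrast to skills or knowledge, because one significant and one non-significant result is not a test of their difference. In a one-mediator model, a target that merely travels with empowerment picks up empowerment's association with the outcome and may be declared a mechanism.
- **The timing.** A mediator must be measured after treatment starts and before the outcome. For advocacy activities the only value before T2 or T3 is the pre-randomization baseline, which cannot carry a treatment effect. The T3 value is concurrent with the 12-month outcome.

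The SAP says that mediation results will give direction for program implementation, so an unsupported statement about which target matters could shape the curriculum.

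**Working it through.** **1. The plan's own figure.** The SAP power section gives n=152, paths a=0.3 (program to mediator), b=0.25 (mediator to outcome), c=0.1 (direct), and two-sided 0.05. I read these as standardized paths, require both a and b to be significant, and treat the two tests as independent.

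- SE(a) = √[(1−0.3²)/150] = 0.0779; z = 3.85; power 0.971.
- R² = 0.25² + 0.1² + 2(0.3)(0.25)(0.1) = 0.0875. SE(b) = √[0.9125/(0.91×149)] = 0.0820; z = 3.05; power 0.862.
- Product: 0.971 × 0.862 = 0.836, against the stated 83%.

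The figure reproduces, as power for one indirect effect through one mediator.

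**2. An inert target in a one-mediator model.** Give a second target no effect of its own, a response a₂ to ASSIST, and a correlation ρ with empowerment after removing treatment. The documents give neither a₂ nor ρ for individual targets, so both are assumed.

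With a₂=0.3 its apparent b path is 0.25ρ. The outcome variance given treatment is 0.25²×0.91 + 0.9125 = 0.9694, so SE = √[(0.9694 − 0.91(0.25ρ)²)/(0.91×149)].

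| ρ | apparent b | SE | z | chance b is significant |
|---|---|---|---|---|
| 0.3 | 0.075 | 0.0843 | 0.89 | 0.144 |
| 0.5 | 0.125 | 0.0839 | 1.49 | 0.319 |
| 0.7 | 0.175 | 0.0833 | 2.10 | 0.556 |

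The z values do not depend on a₂. Multiply by the chance that the a path is significant: 0.971 at a₂=0.3. At a₂=0.15, SE(a) = √[(1−0.15²)/150] = 0.0807, z = 1.86, chance 0.459.

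| a₂ | declared a mediator, ρ = 0.3/0.5/0.7, formula | simulation | joint model |
|---|---|---|---|
| 0.3 | 14/31/54% | 14/30/56% | 0.971×0.05 = 5% |
| 0.15 | 7/15/26% | 6/15/25% | 0.459×0.05 = 2% |

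The weaker response is plausible for knowledge, because Protocol section 2 says that controls "might have some increase in knowledge about adult services, but likely not empowerment". With a binary outcome the simulated rates are somewhat lower: 12/26/46% and 6/13/20%. A small percentile-bootstrap check (400 trials), closer to the SAP's interval, gave 11% at a₂=0.15, ρ=0.5.

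**3. Power of the missing contrast.** This was simulated with empowerment at the SAP paths and inert comparators, using 95% Monte Carlo intervals for the difference of indirect effects. Both contrasts means empowerment against skills and against knowledge.

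| Comparators' response | one contrast, ρ = 0/0.3/0.5/0.7 | both contrasts |
|---|---|---|
| 0.3 | 49/42/31/22% | 32/25/17/10% |
| 0.15 | 66/60/49/33% | 54/46/36/24% |

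If the comparator carries half of empowerment's indirect effect, one contrast has about 10 to 16% power for ρ from 0 to 0.5.

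**4. The timing rule against the schedule.** Advocacy activities has no post-baseline value before T2 and none before T3. Empowerment, skills and knowledge each have one, T1. No target is measured at T2. If the prior wave means the immediately preceding wave, these three therefore also fail the rule for 12-month outcomes. They meet it only if it means the latest earlier post-baseline value.

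**The case against.** The zero-exclusion criterion is not the whole plan. The SAP commits to ignorability analyses and to confounder-adjusted models that confirm findings, and another target is a natural confounder to include. If those models adjust for the other targets, most of the inert-target declarations would disappear, leaving roughly the joint-model rates. This stands: the rates in the working are first-stage rates, and a reader should not infer that the complete plan would report a false mechanism that often. What remains is that the SAP lists no confounders, only considers structural equation models, and states no contrast in any of these steps. The cited mediation steps lie outside the documents.

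The rates are also not necessarily errors. If skills or knowledge act by raising empowerment, the data look the same, the one-mediator result is a correct detection, and the joint model would show no separate effect. All three are measured at T1, so their order cannot be settled.

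On timing, the SAP's sentence speaks of covariates; applying it to the mediator is an inference, though the only reading that serves temporal ordering. A reader might conclude that advocacy activities can never be a lagged mediator. That goes too far: its T3 value precedes outcomes at T5 and T6.

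Finally, the contrasts are weakly powered and may settle nothing. That is true, and it is a reason to limit the claim rather than to make it without a test.

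**Conclusion.** The concern holds on the documents. The Aim 3 hypothesis compares targets and the stated analysis does not, so following the SAP as written cannot support a claim that empowerment rather than skills or knowledge is the mechanism. Advocacy activities cannot be a lagged mediator of 6- or 12-month outcomes, given that the prior-wave rule covers the mediator.

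Neither conclusion needs a numerical assumption. The rates of 14/30/56% (equal response) and 6/15/25% (response 0.15) do. They show how large the first-stage problem could be, not what the trial's error rate is, and they count as errors only if the correlated target does not act through empowerment.

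A reader might also infer that the 83% power is wrong. It is not: it reproduces, and the SAP presents it as power for one indirect effect. It simply does not cover the comparison. Aims 1 and 2 are unaffected. The change should be made, but it bears only on the Aim 3 conclusion.

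**What to change.** 1. **Comparison.** Keep the single-mediator analyses. For each Aim 3 outcome and wave add a joint model with T1 empowerment, skills and knowledge, and bootstrap the difference between empowerment's indirect effect and each of the other two. Name the other targets in the confirmation models. Claim that empowerment differs from skills and knowledge only if both contrasts support it; otherwise report the comparison as inconclusive. State that the model assumes the targets act in parallel, that a target acting through empowerment would show no separate effect, how many contrasts are made, and that their power is limited. Describe the 83% as single-mediator power. As a minimum, drop any claim that empowerment rather than the other targets is the mechanism.
2. **Prior wave.** Define it as the latest earlier post-baseline measurement, which is T1 for T2 and T3 outcomes.
3. **Advocacy activities.** Label its mediation analysis at T3 as concurrent, or as lagged only for outcomes measured at T5 or T6, noting that this follows the offer of ASSIST to controls. Make no contrast claim against it. Reconcile its primary-outcome label in the measures table with its listing as an intervention target in the aims.

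**Cost.** SAP wording and modest extra analysis; no new data. Employment, PSE and service access at T2 and T3 (3×2 = 6), plus social participation and goal attainment at T3 (2), make 8 models and 16 contrasts. The contrasts cover two of the three comparisons that the hypothesis implies, and at the power shown they may well be inconclusive.
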